### 9.2. Analysis Populations

The Intent to Treat (ITT) population is defined as all subjects who are randomized. The Safety population is defined as all randomized subjects who received at least 1 dose of study medication. The Per-Protocol (PP) population is defined as all subjects who are randomized and do not have any major protocol violations. Major protocol violations are defined as:

- Inclusion or Exclusion criteria not met
- Concomitant medications taken during the study that interfere with efficacy
- Did not administer at least 75% of study medication
- Did not complete Week 24 (Visit 9).

### 9.3. Demographic and Baseline Characteristics

Subject demographic and baseline characteristics, including medical and alopecia history, prior medications and therapies and physical examination findings will be summarized using descriptive statistics.

For continuous variables, descriptive statistics (number, mean, standard deviation, standard error, median, minimum, and maximum) will be provided. For categorical variables, subject counts and percentages will be provided. Categories for missing data will be presented, if necessary.

## 9.4. Efficacy Analyses

Hair regrowth is determined based on both percent change from baseline (Baseline SALT – Follow-up SALT/Baseline SALT) and absolute change from baseline (Baseline SALT – Follow-up SALT).

### 9.4.1. Primary Efficacy Analyses

The primary efficacy variable will be the percent change from Baseline (Visit 2) in the SALT score at Visit 9 (Week 24). Missing data for the primary endpoint will be imputed using Last Observation Carried Forward (LOCF) methodology. The analysis will be conducted on the percent change from baseline over time including all visits using a mixed effect model repeated measures (MMRM). The adjusted mean (LS Mean) for percent change from baseline in the SALT score at each visit, estimated from the MMRM, with the estimated standard error and 95% confidence interval (CI), will be presented in tabular and graphic format. The difference in the adjusted means between treatment groups and the associated 95% CI of the difference will be provided. No adjustment for multiplicity will be made. The model will include fixed effect terms for treatment, study visit, baseline SALT score group (<50, ≥50), and treatment by SALT group interaction. The primary analysis will be based on the Intent-to-Treat (ITT) population. Statistical significance for primary efficacy endpoint will be declared if at least one treatment group comparison at the Week 24 visit has a two-sided p-value less than or equal to 0.05.

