### 1.1. Overview of Alopecia Areata

Alopecia areata (AA) is an autoimmune dermatologic condition, which, in its mildest form, is typically characterized by patchy non-scarring hair loss on the scalp and/or body. More severe forms of AA include total scalp hair loss, known as alopecia totalis (AT), and total loss of all the hair on the scalp and body- importantly, including loss of eyebrows, eyelashes, and intranasal hair- known as alopecia universalis (AU). While spontaneous regrowth of hair is common in the milder form of AA (patchy), where the hair loss may wax and wane, in patients with the extensive hair loss of AT or AU, spontaneous hair regrowth is rare. AA affects both males and females across all ethnic groups and ages, and with a lifetime risk of 1.7% (Safavi 1995). About two-thirds of affected individuals are 30 years old or younger at the time of disease onset.

The course of AA is unpredictable and while up to 50% of patients may recover within 1 year even without treatment, most patients will have more than one episode of hair loss (Price 2008). Factors portending a poorer prognosis for regrowth are more extensive hair loss presentations (extensive AA, AT, AU), an ophiasis pattern of hair loss, a long duration of hair loss, a positive family history, the presence of other autoimmune diseases, nail involvement, and young age of first onset (Tosti 2006, Weise 1996). In children, the disease may have a tendency towards worsening with time even if the initial presentation was mild, and the progressively disfiguring nature of the disease can be psychologically devastating. AA is highly associated with numerous psychiatric comorbidities including adjustment disorders, anxiety disorders and depression in both children and adults, and an effective treatment for AT and AU, the more severe forms of the disease, represents a significant unmet medical need (Bilgic 2014, Ruiz-Doblado 2003, Alkhalifah 2010).

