#### 4.3.4. Missing Data and Outliers

For missing clinical assessments, the method of last observation carried forward (LOCF) will be used to impute values. The last non-missing value prior to the missing assessment will replace the missing values. For subjects who terminate early, missing assessment after the date of early termination will be replaced by the LOCF method.

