### **6.2.2. Primary Efficacy Analysis**

Descriptive statistics for the SALT score, change, and percent change from baseline will be presented by analysis visit. Percent change from baseline in SALT over time up to Week 24 will be analyzed using a mixed effect for repeated measures (MMRM) model. This primary analysis will utilize the score with imputation for LOCF and will be based on the ITT population. The model will include fixed effect terms for treatment, study visit, and treatment by study visit interaction. Within-subject variability will be modeled using a compound symmetry covariance structure. The least squares mean (LS Mean) percent change from baseline in the SALT score at each visit, estimated from the MMRM model, with the estimated standard error and 95% confidence interval (CI), will be presented in tabular and graphic format. The difference in the adjusted means between treatment groups and the associated 95% CI of the difference will be provided.

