### **6.2.3. Additional Analyses of the Primary Endpoint**

The statistical methods for the main analysis will be repeated using the PP population. The analysis will also be performed using the observed data without imputation for missing in both the PP population and the ITT population.

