### Section 14.2 Efficacy

#### SALT

13. Table 14.2.1.1 Summary of SALT Score, Change from Baseline, and Percent Change from Baseline by Visit (LOCF), ITT Population
14. Table 14.2.1.1a Summary of SALT Score, Change from Baseline, and Percent Change from Baseline by Visit (Observed), ITT Population
15. Table 14.2.1.2 Analysis of Percent Change from Baseline in SALT Score (LOCF), ITT Population
16. Table 14.2.1.3 Analysis of Percent Change from Baseline in SALT Score (LOCF), PP Population
17. Table 14.2.1.4 Analysis of Percent Change from Baseline in SALT Score (Observed), ITT Population
18. Table 14.2.1.5 Analysis of Percent Change from Baseline in SALT Score (Observed), PP Population
19. Table 14.2.1.6 Analysis of Change from Baseline in SALT Score (LOCF), ITT Population

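### The primary SALT model should be fitted to observed rather than LOCF-filled scores, with an unstructured covariance replacing compound symmetry in the same edit

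*Protocol*

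**What the plan says.** Protocol 9.4.1 (repeated in the synopsis) sets the missing-data rule: "Missing data for the primary endpoint will be imputed using Last Observation Carried Forward (LOCF) methodology". It then names the model: "The analysis will be conducted on the percent change from baseline over time including all visits using a mixed effect model repeated measures (MMRM)". SAP 6.2.2 agrees: "This primary analysis will utilize the score with imputation for LOCF and will be based on the ITT population". SAP 4.3.4 extends the filling to every later visit: "For subjects who terminate early, missing assessment after the date of early termination will be replaced by the LOCF method".

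SAP 6.2.3 adds a run without filling: "The analysis will also be performed using the observed data without imputation for missing in both the PP population and the ITT population". The output is listed in SAP section 9: "Table 14.2.1.4 Analysis of Percent Change from Baseline in SALT Score (Observed), ITT Population". The LOCF counterpart, Table 14.2.1.2, is the primary one. Protocol 9.4.2 itself names only a per-protocol repeat with the same LOCF method.

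SAP 6.2.2 prescribes compound symmetry, and 6.2.3 repeats the main methods, so the observed-data run inherits it. The fixed effects differ between the documents. The protocol has treatment, visit, baseline SALT group and treatment by SALT group. The SAP has treatment, visit and treatment by visit. Neither document defines an estimand or gives a reason for LOCF.

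**The concern.** A likelihood-based repeated-measures model needs no filling; it uses whatever visits each subject has. Filling first assumes that SALT stays fixed after the last score, and it enters the copies as data. Response is scored every four weeks and judged at Week 24, so a score frozen at Week 8 stands in for an outcome 16 weeks later. If response is still building, the Week 24 difference is diluted. If dropout differs by arm, a difference can appear where none exists.

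Unequal dropout is plausible. Protocol 3.4.1.2 has treatment stopped for laboratory findings and subjects withdrawn for ECG findings, and three active arms are compared with placebo. Protocol 9.4.1 declares success if any one Week 24 comparison reaches p ≤ 0.05, without multiplicity adjustment, so distortion in one contrast feeds directly into the conclusion.

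The protocol's own sensitivity analysis cannot test this. The per-protocol set (9.2) excludes anyone who did not complete Week 24, which removes the dropouts whose scores LOCF fills.

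**Working it through.** **The plan's own figure.** SAP 4.1 gives power above 80% for SALT50 and at least 84% for the primary analysis. With 95 × 0.9 = 85.5 completers, about 43 per pooled group, 32% against 6% and two-sided 0.05, exact power with Fisher's test is 84.4%. The figure reproduces. It concerns a pooled responder comparison and says nothing for or against LOCF.

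**Inputs from the documents.** 95 subjects at 1:1:1:1 give 95/4 ≈ 24 per arm. Dropout is 10%. Response visits are Weeks 4, 8, 12, 16, 20 and 24.

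**Assumptions.** Linear accrual to a 25-point Week 24 difference; no mean change on placebo; dropout d spread evenly over the six visits and unrelated to outcome; baseline carried forward if there is no later score.

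**Dilution.** The last score before dropout falls at Week 0, 4, 8, 12, 16 or 20, mean 10. A dropout therefore keeps 10/24 = 0.417 of the true change, and an arm keeps 1 − 0.583d.

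| Dropout, active/placebo | Formula | LOCF, simulated | Observed data, simulated |
|---|---|---|---|
| 10%/10% | 25 × 0.942 = 23.5 | 23.3 | 24.8 |
| 20%/20% | 25 × 0.883 = 22.1 | 21.5 | 24.4 |
| 25%/10% | 25 × 0.854 = 21.4 | 21.2 | about 25 |
| 30%/10% | 25 × 0.825 = 20.6 | 20.8 | 25.3 |

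Rows 1, 2 and 4 are 300 simulated trials each (random-slope SD 28, residual SD 8, both runs with compound symmetry). Row 3 is 3,000 trials (slope SD 35, residual SD 6, Week 2 included): a plain LOCF difference in means against maximum likelihood under missing at random. Two variations bracket the formula. Counting the Week 2 score gives a mean last week of 62/7 = 8.86 and a loss of 0.631d. If every leaver is scored at withdrawal, at a time uniform over 24 weeks, the loss is 0.5d. At 10% dropout the loss is thus 5.0% to 6.3%.

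**Unequal dropout, no true difference.** If both arms improve by 25 points with dropout of 30% and 10%, the false difference is 25 × 0.583 × (0.30 − 0.10) = 2.9 points, or 3.2 with the 0.631 factor. A simulation gave 3.4. It runs against the arm with more dropout.

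**Copied rows.** Two arms give 48 × 6 = 288 records. A dropout misses 3.5 visits on average, so 48 × 0.10 × 3.5 ≈ 17 records are copies at 10% dropout.

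**Standard error.** With slope SD 35, residual SD 6 and 10% dropout (1,500 trials), the plain LOCF contrast at Week 24 has mean estimated SE 9.86 against empirical SD 9.88, and rejects 4.9% of the time under no difference. Filling alone does not understate it. Under compound symmetry the model SE is 6.13 against 9.88 with LOCF, and 6.30 against 10.60 on observed data.

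Type I error for one Week 24 comparison, 10% dropout, 300 trials:

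| Model | Spread grows over time | Constant variance |
|---|---|---|
| LOCF, compound symmetry | 16.7% | 4.7% |
| Observed, compound symmetry | 18.0% | 5.0% |
| Observed, unstructured | 3.7% | 5.3% |

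Monte Carlo error is about ±2.5 points near 5% and ±4 points near 17-18%.

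**The case against.** The strongest reply is that the effect is small under the only dropout rate in the documents. At 10% the loss is about 1.5 of 25 points, roughly 0.15 of a standard error near 10, and the observed-data analysis is already prespecified and tabulated, so readers of an initial Phase 2 study will see any dependence on LOCF. That stands as a limit on size. It does not explain why the weaker analysis should be the one that decides success.

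It is also fair that missing at random cannot be verified, least of all with safety-driven withdrawals, and that the choice of primary run partly depends on the estimand. That is a reason to state the estimand and add a departure analysis, not to keep LOCF.

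Three stronger readings are tempting and unsupported:

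- A reader might infer that LOCF makes the standard error too small. The check above does not show that; compound symmetry does it, and promoting the observed-data run unchanged would carry the problem along.
- A reader might take the statement in protocol 1.1 that "up to 50% of patients may recover within 1 year even without treatment" as proof that untreated scores move in this trial. It describes alopecia areata in general. The same section calls spontaneous regrowth rare in AT and AU, about 45 of the 95 subjects have AT or AU, and entry requires stable loss for at least 6 months.
- A reader might infer a likely false positive from the unequal-dropout case. A mean improvement of 25 points with SD 35 on placebo implies about 24% SALT50 responders (normal approximation, z = 25/35 = 0.71), against at most 6% planned for placebo and 400 mg. And with more dropout on active, the shift works against the drug.

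**Conclusion.** The primary model is fitted to filled data that it does not need, and the plan gives no reason for it. The expected distortion is dilution: about 5-6% of the Week 24 difference at the planned dropout, about 12-15% at 20% dropout or 25%/10%, and a false shift of about 3 points when dropout is 30% against 10% and true improvement is equal. These sizes depend on linear accrual, a 25-point difference and dropout unrelated to outcome. Dropout above 10% or unequal between arms is assumed, not planned. The direction can reverse if dropouts keep early gains that they would have lost.

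Changing the primary run is worthwhile but incomplete without the covariance. If spread grows over time, compound symmetry has the larger effect on inference: type I error of about 17-18% in either run, against about 4% with an unstructured matrix. If variance is constant, all three models hold near 5%. The documents do not say which pattern to expect.

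**What to change.** In protocol 9.4.1 and SAP 6.2.2-6.2.3, before unblinding:

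1. Make the observed-data ITT model (Table 14.2.1.4) primary and move the LOCF version (Table 14.2.1.2) to sensitivity.
2. Replace compound symmetry with an unstructured covariance, a prespecified fallback if it does not converge, and Kenward-Roger degrees of freedom.
3. Include treatment by visit, so that the Week 24 contrast is specific to Week 24, and reconcile the remaining fixed effects. SAP section 7 currently says that the two documents agree.
4. State the estimand and add at least one sensitivity analysis that departs from missing at random, such as a reference-based or tipping-point analysis.
5. If percent change in ALODEX is to follow the primary method, add an observed-data table. SAP section 9 lists only LOCF tables for it (14.2.2.1 to 14.2.2.3). The SALT and ALODEX subgroup model tables are also LOCF only.

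For SALT, both runs and their tables are already planned. The costs are a Week 24 estimate about 4-10% more variable (empirical SD 10.39 against 9.97 at 10% dropout, 10.50 against 9.52 at 20%), modest extra programming, and another change to wording that Amendment 4 has just set.

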**Statistical Methods**

The primary efficacy variable will be the percent change from Baseline in the SALT score at Week 24 (Visit 9). This represents the percentage of hair regrowth. It will be calculated as the change from baseline (Visit 2) to Week 24 (Visit 9), divided by the baseline and expressed as a percentage.

Missing data for the primary endpoint will be imputed using Last Observation Carried Forward (LOCF) methodology. The analysis will be conducted on the percent change from baseline over time including all visits using a mixed effect model repeated measures (MMRM). The adjusted mean (LS Mean) for percent change from baseline in the SALT score at each visit, estimated from the MMRM, with the estimated standard error and 95% confidence interval (CI), will be presented in tabular and graphic format. The difference in the adjusted means between treatment groups and the associated 95% CI of the difference will be provided. No adjustment for multiplicity will be made. The model

will include fixed effect terms for treatment, study visit, baseline SALT score group (<50, >=50), and treatment by baseline SALT group interaction. The primary analysis will be based on the Intent-to-Treat (ITT) population. Statistical significance for primary efficacy endpoint will be declared if at least one treatment group comparison at the Week 24 visit has a two-sided p-value less than or equal to 0.05.

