## 9. STATISTICS

### 9.1. Sample Size and Power Calculations

The planned sample size is 95 enrolled subjects with approximately 45 subjects enrolled with AT or AU.

The sample size estimate was based on published results from a similar study (Crispin et al. 2016) where 32% of subjects receiving active drug achieved at least a 50% reduction in hair loss (SALT50) under similar conditions. For the current study, the primary efficacy analysis is mean percent change in hair loss, evaluated using SALT scores. That analysis is expected to have greater statistical sensitivity than the SALT50 responder analysis, which is also a secondary efficacy analysis in the current study.

We assume the pooled results of 600mg and 800mg treatment groups in the current study will achieve the same or higher SALT50 response rate (32%) as the published results above, and pooled Vehicle plus 400mg treatment groups will not achieve more than a 6% SALT50 response rate. Based on a comparison of those two pooled groups, the current study is anticipated to have no less than 80% power with a 10% subject dropout rate for the SALT50 analysis. Because the primary efficacy analysis of mean percent change in hair loss using SALT scores is expected to be more sensitive than the SALT50 responder analysis, the power for the primary analysis is also expected to be no less than 80%.

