### **4.3. HANDLING OF DATA**

#### **4.3.1. Strata and Covariates**

No stratified analyses are planned.

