#### **4.3.2. Examination of Subject Subsets**

The baseline SALT score group ( $< 50$ ,  $\geq 50$ ) will be used for subset analyses. Additionally, duration of current episode ( $< 4$  years,  $\geq 4$  years) will be used for subset analyses. The details of the subset analyses are given in the statistical analysis section.

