## **7. CHANGES IN THE PROTOCOL-SPECIFIED ANALYSES**

All analyses specified in the SAP are consistent with those specified in the protocol. Should any deviations from the analyses specified in the authorized statistical analysis plan arise, such deviations will be documented in the final clinical study report.

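### The protocol's primary model crosses treatment with baseline SALT group without stating the LS-mean weights, and the SAP specifies a different primary model while declaring agreement

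*Protocol*

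**What the plan says.** Protocol 9.4.1 lists the fixed effects of the primary MMRM as treatment, study visit, "baseline SALT score group (<50, ≥50), and treatment by SALT group interaction". The synopsis gives the same terms. Neither lists treatment-by-visit. On the estimate, both say: "The difference in the adjusted means between treatment groups and the associated 95% CI of the difference will be provided". Success requires that at least one comparison at Week 24 "has a two-sided p-value less than or equal to 0.05". How LS means are averaged over the SALT groups is not stated. Protocol 9.4.2 applies the same method to the per-protocol sensitivity analysis and to percent change in ALODEX.

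SAP 6.2.2 reads differently: "The model will include fixed effect terms for treatment, study visit, and treatment by study visit interaction". SAP 4.3.1 adds "No stratified analyses are planned", and SAP 4.3.2 and 6.2.7 use the <50/≥50 split for subset analyses only. SAP section 7 then states: "All analyses specified in the SAP are consistent with those specified in the protocol".

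On the size of the SALT groups, protocol 9.1 says only: "The planned sample size is 95 enrolled subjects with approximately 45 subjects enrolled with AT or AU". Protocol Tables 5 and 6 define patchy disease as 30% to 95% scalp hair loss and AT/AU as more than 95%.

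**The concern.** Once treatment is crossed with SALT group, the model has a separate treatment effect in each group. The single LS-mean difference reported as primary is then a weighted average of two effects, and the weights are part of the definition of the estimate. The usual software convention gives each factor level the same weight, so the <50 group would count for one half however few subjects it holds.

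The groups are unlikely to be equal. All of the roughly 45 AT/AU subjects fall in ≥50. Only patchy subjects with SALT from 30 to 49 fall in <50. If they are few, the precision of the primary comparison depends on a handful of subjects per arm. If the effect differs by group, the estimate also moves away from the effect in the enrolled mix.

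The conflict with the SAP adds to this. Someone must choose between two primary models, and SAP section 7 does not acknowledge a choice. Resolving it by carrying the protocol's terms into the SAP, or by only adding treatment-by-visit to the protocol model, would leave the weights undefined.

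**Working it through.** **The plan's own power figure.** Inputs from protocol 9.1 and SAP 4.1: 32% versus 6% SALT50 response, N = 95, 10% dropout, two pooled groups, so 95 × 0.9 / 2 = 42.75 per group. At two-sided 0.05, power is 87.9% by the pooled z test, 81.0% with continuity correction and 84.4% by Fisher's exact test at 43 per group. The protocol's floor of 80% and the SAP's 84% are both reproducible. They refer to pooled arms on a responder endpoint, and neither reflects the SALT-group interaction.

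**Variance under the protocol model.** Let each arm have n subjects, a share p of them <50, and a common variance σ². LOCF completes the visits, so subject counts drive the comparison.

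- Equal weights, variance of one arm's mean: (σ²/4) × [1/(np) + 1/(n(1−p))] = σ²/[4np(1−p)].
- Proportional weights: σ²/n.
- Ratio: 1/[4p(1−p)]. Information lost: 1 − 4p(1−p).
- A nominal 80% power becomes Φ(2.80 × √[4p(1−p)] − 1.96) if the effect is the same in both groups. The 80% starting value is illustrative.

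**Share below 50.** The documents bound it but do not give it. With about 45 AT/AU subjects, at most about 50 of 95 can be <50. If patchy SALT is assumed uniform on 30 to 95, the number is 50 × 20/65 = 15.4, or 16.2% of 95 and about 4 per arm.

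| <50 share | Subjects of 95 | 4p(1−p) | Information lost | SE multiplier | Nominal 80% power becomes |
|---|---|---|---|---|---|
| 10% | 9.5 | 0.36 | 64% | 1.67 | 39% |
| 16.2% (uniform) | 15.4 | 0.543 | 46% | 1.36 | 54% |
| 20% | 19 | 0.64 | 36% | 1.25 | 61% |
| 25% | 23.8 | 0.75 | 25% | 1.15 | 68% |
| 30% | 28.5 | 0.84 | 16% | 1.09 | 73% |
| 40% | 38 | 0.96 | 4% | 1.02 | 78% |
| 52.6% (all patchy) | 50 | 0.997 | 0.3% | 1.00 | 80% |

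The formula takes the same share in every arm. Allowing for chance imbalance over 4,000 simulated allocations, the median loss at 16.2% is about 50%.

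**Empty cells.** No stratification by SALT group is described. With 24 per arm, the chance that some arm has no <50 subject is 1 − [1 − (1−p)^24]^4: 5.6% at a 16.2% share and 28% at 10%. That arm's LS mean would then be non-estimable.

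**Effects that differ by group.** Suppose, for illustration only, effects of −40 (<50) and −15 (≥50) at the 16.2% share. The enrolled mix gives 0.162 × (−40) + 0.838 × (−15) = −19.05. Equal weights give −27.5, which is 1.44 times as large, while the SE is 1.36 times as large. The power index becomes 2.80 × 1.44/1.36, or about 2.98 before rounding, and power is Φ(2.98 − 1.96), about 85%. The estimate shifts but power is not lost. The shift and the loss rest on different assumptions and should not be added together.

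**SAP model.** It has no SALT term, so LS means involve no averaging over SALT groups and the loss is zero.

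**The case against.** The strongest objection is that the SAP's primary model is free of the problem. If SAP 6.2.2 is what gets run, no half weight and no loss occur, and the SALT split already sits in the subset analyses. That stands. It does not close the matter, because SAP section 7 claims agreement and so does not record that the protocol's terms were dropped.

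A reader might infer that the plan itself gives the <50 group half the weight. It does not. Equal weighting is a software default, and what the plan lacks is any statement of weights.

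A reader might also infer that nearly half the information is lost. A loss of 45% to 50% needs a <50 share of about 14.6% to 16.5% (14 to 16 subjects). The documents allow anything up to about 50 subjects, where the loss is negligible. In the other direction, a loss below 10% would need about 33 of the 50 patchy subjects in the lowest 20 points of a 65-point range. That is possible, but the plan does not show it.

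Finally, it would be wrong to say that the estimate describes patients whom the trial does not enrol. SALT 30 to 49 is expressly eligible under inclusion criterion 4, so the issue is only how much that group counts.

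**Conclusion.** The firm finding is textual. The protocol and the SAP specify different primary models, the SAP says that they agree, and the protocol model leaves the weights in its primary estimate undefined. The numerical consequence is conditional on three things: that the protocol model is run, that default equal weights are used, and that the <50 group is small. Under those conditions, with equal variances and a common effect, the loss ranges from about 64% at a 10% share to almost nothing when every patchy subject is below 50. The 46% figure belongs to the uniform-SALT assumption alone. If effects differ by group, the estimate moves away from the enrolled mix and the power loss need not occur. This should be settled before unblinding, because the choice of model and weights can change the primary result. The documents do not support a claim that the trial as planned has lost a known amount of power.

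**What to change.** Reconcile protocol 9.4.1 and the synopsis with SAP 6.2.2 on one primary model: treatment, visit, treatment-by-visit and baseline SALT as a main-effect covariate, with no treatment-by-SALT-group term. Treatment-by-visit is needed because without it the protocol's treatment difference is the same at every visit, although the success rule is tied to Week 24. The SAP in turn gains a baseline SALT term, and SAP 4.3.1 and section 7 should be updated to match. Leave effect by SALT group to the subset analyses in SAP 4.3.2 and 6.2.7.

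If the interaction is kept, state that LS means use observed margins, and say what is done if an arm has no subject below 50, since observed margins do not make that arm's mean estimable. Carry the decision through to the per-protocol and ALODEX percent-change analyses, which inherit the method.

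The cost is wording and one model option. Baseline SALT is already collected, and no further data or subjects are needed.
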